10.5 Data Analyses Plans

10.5.1 Primary Analysis

Simon's 2-stage for efficacy

We plan a Simon's 2-stage MiniMax design evaluation of the combination of blinatumomab and pembrolizumab in relapsed or refractory B-cell ALL with >50% blasts in the marrow.

We assessed the sample size for studying using overall response rate (CR + CRh). From recent large Phase II study including 189 subjects with relapsed/refractory B-lineage ALL, ORR (CR + CRh) to blinatumomab monotherapy was approximately 29% in patients with >50% lymphoblasts in the bone marrow (Topp et al. 2015). Response rates for PD-1 inhibitors in relapsed or refractory ALL are unknown but given mechanism of action it likely approaches zero.

An absolute increase in the overall response rate of 25 percentage points (i.e. to 54% ORR in patients evaluable for efficacy) or greater will demonstrate sufficient activity to consider the regimen for further study.

To calculate sample sizes for Stage 1 and Stage 2 we used a probability of type I error (α) = 0.05 and a power ($1-\beta$) = 0.80 with $p_0=0.29$ and $p_1=0.54$.

The null hypothesis that the true response rate is 0.29 will be tested against a one-sided alternative. In the first stage, 18 patients evaluable for efficacy will be accrued. If there are 7 or fewer responses in these 18 patients, the study will be stopped. Otherwise, 6 additional patients will be accrued for a total of 24 patients evaluable for efficacy of the combination. The null hypothesis will be rejected if 11 or more responses are observed in 24 evaluable patients. This design yields a type I error rate of 0.05 and power of 0.80 when the true response rate is 0.54. The likelihood of early termination is 0.88, if the null hypothesis is true.

Safety rules

At the time of the Stage 1 efficacy analysis, all patients will be reviewed again for DLTs as defined in Section 5.1.4 occurring at any time during therapy.

A DLT rate exceeding 0.3 will be considered unacceptable. The first 3, 6, 12, and 24 patients will be monitored for DLTs. The first 6 patients will be monitored every other week. The next 6 patients will be monitored monthly. Subsequent patients will be monitored every other month.

k	1	2	3	4
n_k	3	3	6	12

N_k	3	6	12	24
r_k	1	1	3	5

Table: Monitoring design for DLTs. The stage is denoted by k . The number of patients accrued during and up to stage k are denoted by n_k and N_k respectively. The critical value at stage k is denoted by r_k .

If the critical value r_k for any stage is exceeded, study enrollment will be suspended and a discussions between the study chair, study principal investigators, the DSMB for the study, and the FDA will occur to discuss amending or closing the study.

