5. TREATMENT PLAN

5.1 Treatment dosage and administration

5.1.1 Treatment summary

The study will be conducted in 2 stages:

Stage 1 is to ensure safety of pembrolizumab in combination with blinatumomab.

Dose Limiting Toxicity (DLT) is defined as a clinically significant adverse event that is considered by the investigator to be probably or definitely related to pembrolizumab or the combination of pembrolizumab and blinatumomab occurring within 42 days of the first dose of pembrolizumab on Day 15 of Cycle 1 as follows:

- Any Grade 3-5 non-hematologic toxicity EXCEPT:
 - Grade 3 cytokine release syndrome that resolves in 7 days or less
 - Grade 3 neurotoxicity that resolves in 7 days or less
 - Grade 3 infections
 - Grade 3 or 4 febrile neutropenia unless deemed by investigator to be definitely related to pembrolizumab
 - Grade 3 or 4 laboratory abnormalities unless they warrant temporary discontinuation of pembrolizumab or permanent discontinuation of blinatumomab (see tables, 5.7.1 and 5.7.2)
 - Grade 3 or 4 lymphopenia
- Any clinically significant toxicity that precludes administration of the next scheduled dose for more than 14 days

If no DLTs are experienced in the first 3 subjects then enrollment will advance Stage 2. If 1 DLT is noted in the first 3 subjects then 3 additional subjects will be enrolled. If no further DLTs are noted in the additional 3 subjects then enrollment will proceed to Stage 2. If 2 or more DLTs are noted at the proposed pembrolizumab dose level and schedule then enrollment will be placed on hold and a dose reduction or schedule change will be considered after discussion of investigators.

The DLT monitoring period will be 42 days starting on Day 15 of Cycle 1. Subjects withdrawing from investigational treatment during the DLT monitoring period for a reason that is definitely unrelated to toxicity of the study agent (e.g. disease progression, patient withdrawal of consent) will be deemed not evaluable for DLT determination and will be replaced. All subjects in Stage 1 will need to complete the DLT monitoring period prior to proceeding with Stage 2.

Stage 2 of the study will include an expansion cohort of up to 21 additional subjects (for a total of 24 subjects) to evaluate the efficacy of the combination of blinatumomab and pembrolizumab.

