5.1.4 Stage I – Dose limiting toxicity definition and stopping rules

To determine the safety of pembrolizumab in combination with blinatumomab in patients with acute lymphoblastic leukemia, the combination will be administered to 3-6 patients with relapsed or refractory B-lineage acute lymphoblastic leukemia.

Toxicity will be graded according to the National Cancer Institute (NCI) Common Toxicity Criteria for Adverse Events (CTCAE) version 4.03. Adverse events will be assessed continuously throughout therapy.

Dose Limiting Toxicity (DLT) is defined as a clinically significant adverse event that is considered by the investigator to be probably or definitely related to pembrolizumab or the combination of pembrolizumab and blinatumomab occurring within 42 days of the first dose of pembrolizumab on Day 15 of Cycle 1 as follows:

- Any Grade 3-5 non-hematologic toxicity EXCEPT:
 - Grade 3 cytokine release syndrome that resolves in 7 days or less
 - Grade 3 neurotoxicity that resolves in 7 days or less
 - Grade 3 infections
 - Grade 3 or 4 febrile neutropenia unless deemed by investigator to be definitely related to pembrolizumab
 - Grade 3 or 4 laboratory abnormalities unless they warrant temporary discontinuation of pembrolizumab or permanent discontinuation of blinatumomab (see tables, 5.7.1 and 5.7.2)
 - Grade 3 or 4 lymphopenia
- Any clinically significant toxicity that precludes administration of the next scheduled dose for more than 14 days

Decision to proceed to Stage 2 of the study will be made as follows below.

Number of Patients with DLT	Decision Rule
0 out of 3	Proceed to Stage 2 of study.
1 out of 3	Enter at least 3 more patients. 
 If 0 of these 3 patients experience DLT, proceed to Stage 2 of study If 1 or more of this group suffer DLT, then study will be placed on hold. Decision regarding dosing of pembrolizumab and continuation of study will be made after discussion between sponsors and investigators.
≥ 2	Study will be placed on hold and the FDA notified. Decision regarding dosing of pembrolizumab and continuation of study will be made after discussion between sponsors, investigators and FDA.
≤ 1 out of 6	Proceed to Stage 2 of study.

Subjects withdrawing from investigational treatment during the DLT monitoring period for a reason that is definitely unrelated to toxicity of the study agent (e.g. disease progression, patient withdrawal of consent) will be replaced.

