5.7 Toxicities and Dosing Delays/Dose Modifications

Any patient who receives treatment on this protocol will be evaluable for toxicity. Each patient

will be assessed for the development of toxicity except cytokine release syndrome (see below, grading/management per Lee et al. Blood 2014) according to the NCI Common Toxicity Criteria for Adverse Events (CTCAE), version 4.03. Dose adjustments should be made according to the system showing the greatest degree of toxicity. As Blinatumomab is an approved treatment for this indication, reducing or withholding pembrolizumab should be considered as the first option in response to a toxicity prior to adjusting the Blinatumomab dosing.

Adverse events (both non-serious and serious) associated with pembrolizumab exposure may represent an immunologic etiology. These adverse events may occur shortly after the first dose or several months after the last dose of treatment. Pembrolizumab and blinatumomab must be withheld for drug-related toxicities and severe or life-threatening AEs as per Tables below. See Section 5.6.1 in Events of Clinical Interest Guidance Document for additional supportive care guidelines.

All dose adjustments presume that the toxicity is determined by the investigator to be possibly, probably, or definitely related to blinatumomab, pembrolizumab, or both. Withholding the dose and dose adjustments should not occur if toxicity is felt unlikely to be or definitely not related to study blinatumomab, pembrolizumab, or both.

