10.4 Evaluable Subjects and Subject Replacement

Stage 1 (Safety evaluation)

Evaluable subjects are defined as any patient receiving the combination of blinatumomab and pembrolizumab starting day 15 of Cycle 1. The DLT monitoring period will be 28 days starting Day 15 of Cycle 1. Subjects withdrawing from investigational treatment during the 28 day DLT monitoring period for a reason that is definitely unrelated to toxicity of the study agent (e.g. disease progression, patient withdrawal of consent) will be replaced for the safety analysis. 3-6 patients will be enrolled at in Stage 1 as determined by 3+3 rules. These patients will also be evaluated for efficacy.

Stage 2

Stage 2 of the study will include an expansion cohort of up to 21 additional subjects for a total of 24 subjects to evaluate the efficacy of the combination of blinatumomab and pembrolizumab. All patients receiving combination therapy starting day 15 of cycle 1 will be considered evaluable for overall response rate of entire population, RFS and OS.

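### Sections 5.1.4 and 10.5.1 conflict on whether toxicity more than 42 days after the first pembrolizumab dose counts toward the DLT suspension rule

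*Combined protocol and SAP*

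**What the plan says.** - **Any-time review.** Under the safety rules in 10.5.1, at the Stage 1 efficacy analysis, "all patients will be reviewed again for DLTs as defined in Section 5.1.4 occurring at any time during therapy". In that section Stage 1 is the first stage of the Simon design, 18 patients evaluable for efficacy. Elsewhere the same label is used for the 3-6 patient safety run-in.
- **DLT definition.** Section 5.1.4 builds a time limit into the definition: the event must be one "occurring within 42 days of the first dose of pembrolizumab on Day 15 of Cycle 1 as follows". Section 5.1.1 repeats the definition and adds "The DLT monitoring period will be 42 days starting on Day 15 of Cycle 1".
- **A third statement.** Section 10.4 says "The DLT monitoring period will be 28 days starting Day 15 of Cycle 1".
- **Suspension rule.** Section 10.5.1 says "A DLT rate exceeding 0.3 will be considered unacceptable" and "The first 3, 6, 12, and 24 patients will be monitored for DLTs". The critical values r_k are 1, 1, 3 and 5. If the critical value "for any stage is exceeded, study enrollment will be suspended" and the study leadership, the DSMB and the FDA discuss amending or closing the study. No window is given for the events counted.
- **Delayed toxicity.** Section 5.7 says of adverse events associated with pembrolizumab: "These adverse events may occur shortly after the first dose or several months after the last dose of treatment".

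**The concern.** In 5.1.4 the 42-day limit is part of what makes an event a DLT. The 10.5.1 sentence imports that definition and in the same breath asks for events at any point in therapy. Taken literally, the two conditions cannot both apply to an event on, say, Day 100.

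This matters because r_k is the only numerical safety boundary that operates after the run-in. Two people holding the same data can reach different counts. One drops everything after about Day 57 and the other keeps it, so the decision to suspend enrollment can depend on which clause is read. The 28- versus 42-day mismatch is a separate inconsistency. Settling it would still leave open what counts toward r_k later in therapy.

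**Working it through.** The documents give no operating characteristics for the r_k table, so there is no stated figure to reproduce.

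**1. What the window covers.** Pembrolizumab is given on Days 15 and 36 of each 42-day cycle, for up to 5 cycles (5.1.3). Dose days are 42(c-1)+15 and 42(c-1)+36 for c = 1 to 5: Days 15, 36, 57, 78, 99, 120, 141, 162, 183 and 204. The 42-day window ends at about 15 + 42 = Day 57. Doses 1 and 2 precede that day, and the other 8 of 10 fall on or after it. As a share of the interval from first to last dose, 42/(204-15) = 42/189 = 0.22.

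**2. Does the any-time review reach the boundary?** The review is tied to the 18-patient efficacy analysis. The r_k looks are at 3, 6, 12 and 24, so 18 has no critical value. No sentence says that events found at the review are added to the count used at 24, or that late events in earlier patients revise the count. The 6 patients accrued afterwards have no stated any-time review.

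**3. The rule's behaviour.** Suspension occurs if cumulative DLTs exceed 1 of 3, 1 of 6, 3 of 12 or 5 of 24. I used exact binomial probabilities carried forward over the four looks. At a counted rate of 0.40, the first look gives 3(0.4²)(0.6) + 0.4³ = 0.352, and all four looks sum to 0.352 + 0.415 + 0.093 + 0.114 = 0.974. At counted rates of 0.10, 0.20 and 0.30 the totals are 0.132, 0.501 and 0.842.

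**4. Illustration with treatment stopping as planned.** The assumptions are:
- a constant hazard from Day 15, with P the cumulative risk if treated to Day 204;
- every patient treated at least to Day 57;
- non-responders stopping at Day 78 or 84, since 5.1.3 takes patients without CR/CRh after 2 cycles off study;
- response rates R of 0.29 and 0.54, the p0 and p1 of 10.5.1;
- response and toxicity independent, and on-therapy events known at each look.

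The counted rate is:
- 42-day events only: 1-(1-P)^(42/189).
- All on-therapy events: R·P + (1-R)·[1-(1-P)^((s-15)/189)], with s = 78 or 84.

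For P = 0.40:
- 42-day only: 1-0.60^0.222 = 0.107, suspension 0.15.
- Low end (R = 0.29, s = 78): 0.29(0.40) + 0.71(0.157) = 0.227, suspension 0.61.
- High end (R = 0.54, s = 84): 0.54(0.40) + 0.46(0.170) = 0.294, suspension 0.83.

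For P = 0.30:
- 42-day only: 1-0.70^0.222 = 0.076, suspension 0.08.
- Low end: 0.29(0.30) + 0.71(0.112) = 0.167, suspension 0.36.
- High end: 0.54(0.30) + 0.46(0.122) = 0.218, suspension 0.58.

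**5. Check without a hazard model.** Let a share f of DLTs fall inside 42 days. The documents do not give f. Here the true rate is the actual per-patient on-therapy rate, so the counted rate is f times it.

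| True on-therapy rate | f = 1 | f = 0.75 | f = 0.50 | f = 0.25 |
|---|---|---|---|---|
| 0.30 | 0.842 | 0.603 | 0.296 | 0.074 |
| 0.40 | 0.974 | 0.842 | 0.501 | 0.132 |

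**The case against.** A reader might infer that late toxicity cannot count at all, that the rule is blind to it, and that the any-time review can find nothing new. The documents do not support any of these.

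- The any-time clause can be read as keeping the 5.1.4 criteria on type, grade and attribution while lifting the time limit. Otherwise the clause has no effect. No passage excludes late events from the r_k count.
- Even on the literal reading, the review could find in-window events in patients enrolled after the run-in, events since re-attributed, or events on days 29-42 missed by a site following the 28-day period in 10.4.
- Late toxicity is monitored by other routes: continuous adverse event assessment (5.1.4), SAE and event-of-clinical-interest reporting to 90 days after treatment (8.8.1.1, 8.8.1.2), prompt DSMB Chair notification of related deaths (8.8.1) and DSMB oversight (11.8).
- A larger contrast is also tempting. With all 24 patients treated to Day 204, suspension falls from 0.97 to 0.15 at a rate of 0.40, and from 0.84 to 0.08 at 0.30. That ignores the planned exit of non-responders after 2 cycles. Transplant exits would narrow the gap further.

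All of this stands against the stronger claims. It does not settle the count. The other routes carry no numerical boundary. The generous reading also leaves the any-time review at a sample size with no critical value and no stated link to r_k.

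**Conclusion.** The plan is contradictory on whether DLT-type toxicity after about Day 57 counts toward suspension. It does not establish that such toxicity is excluded. The conflict lies in the only numerical safety boundary after the run-in, in a trial whose own text expects delayed immune events, so it should be fixed.

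Under the stated assumptions, the choice of reading moves the chance of suspension between 0.15 and 0.61-0.83 for a full-course rate of 0.40, and between 0.08 and 0.36-0.58 for 0.30. These figures show sensitivity and are not predictions. They rest on a constant hazard and on the assumed stopping days and response rates. The true share of late DLTs is not in the documents, and transplant exits, which are not modelled, would reduce the difference.

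**What to change.** Reconcile 5.1.1, 5.1.4, 10.4 and 10.5.1 in one edit:

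1. In 5.1.4, separate the event criteria (type, grade, attribution) from the time window.
2. State one window for the Stage 1 proceed/hold decision, resolving 28 against 42 days. Which applies is for the sponsor and investigators to decide.
3. State separately the window for events counted against r_k and the 0.3 limit, and make it consistent with the any-time clause in 10.5.1. If it is to run beyond therapy, first reconcile the collection periods: 30 days in 8.1 against 90 days in 8.8.1.1 and 8.8.1.2.
4. Say that events found in the any-time review, including late events in earlier patients, update the running r_k count. Say also how the patients accrued after the 18-patient analysis are reviewed.
5. Report the operating characteristics of r_k = 1, 1, 3, 5 for the window chosen, so that the boundaries and the 0.3 limit can be seen to suit it.

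The cost is a few sentences and a short calculation. For events on therapy, no new data are needed. The downside is a higher chance of suspension for review if later events count.

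### The DLT looks at 12 and 24 patients count patients accrued, although only patients who have started pembrolizumab can have a DLT, so the suspension rule is weakened if applied as written

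*Combined protocol and SAP*

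**What the plan says.** The safety rules in section 10.5.1 state that "A DLT rate exceeding 0.3 will be considered unacceptable" and that "The first 3, 6, 12, and 24 patients will be monitored for DLTs". The table gives increments n_k of 3, 3, 6 and 12, totals N_k of 3, 6, 12 and 24, and critical values r_k of 1, 1, 3 and 5. The legend defines the two counts with the words "The number of patients accrued during and up to stage" k. If r_k "for any stage is exceeded, study enrollment will be suspended", and discussion with the DSMB and FDA follows. No error rate or suspension probability is stated for this rule.

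Sections 5.1.1 and 5.1.4 define a DLT as related to pembrolizumab or to the combination and "occurring within 42 days of the first dose of pembrolizumab on Day 15 of Cycle 1".

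For Stage 1, section 10.4 says "Evaluable subjects are defined as any patient receiving the combination of blinatumomab and pembrolizumab starting day 15 of Cycle 1". A patient who withdraws during the DLT period for a clearly unrelated reason "will be replaced for the safety analysis"; section 5.1.1 adds that such a patient "will be deemed not evaluable for DLT determination and will be replaced". Section 5.1.1 also requires every Stage 1 subject to finish the DLT period before Stage 2 begins.

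For Stage 2, section 10.4 makes combination recipients evaluable for response, RFS and OS, and does not mention DLTs. Sections 5.7 and 7.1.1 make every treated patient evaluable for toxicity, which includes those who received blinatumomab alone.

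**The concern.** The numerator and denominator of the later looks refer to different groups. A patient who leaves during Days 1 to 14 cannot contribute a DLT, but has been accrued. So has a patient enrolled shortly before the look, who is at least 14 days from the first pembrolizumab dose and then has the DLT window still to run.

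The critical values would therefore be applied to fewer patients at risk than N_k shows, and an unacceptable DLT rate would be less likely to trigger suspension. Some early loss is foreseeable. The tables in section 5.7.1 take patients off protocol therapy for Grade 4 cytokine release syndrome, Grade 4 neurotoxicity and Grade 3 or 4 seizure, all of which could occur on blinatumomab alone. Section 1.2.1 associates cytokine release with high disease burden, and that is the population enrolled.

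**Working it through.** **Inputs.** From section 10.5.1: r = (1, 1, 3, 5), with suspension when the cumulative DLT count exceeds r_k, and an unacceptable rate above 0.3. Assumed: the number of patients 7 to 24 who never receive pembrolizumab (0, 2, 3 or 4), with the first six all exposed because of the Stage 1 rules.

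**Plan's own figure.** There is none to reproduce for the DLT rule. As a check on method, exact enumeration of the Simon design in the same section gives type I error 0.0499, power 0.801 and early-termination probability 0.880, in agreement with the stated 0.05, 0.80 and 0.88.

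**Formula.** Let m_k be the exposed patients added at look k and f_k(s) the probability of reaching look k with s cumulative DLTs. Then f_k(s) = Σ f_{k−1}(j) × Bin(s − j; m_k, p), summed over j ≤ r_{k−1}. The probability of suspending at look k is the sum of f_k(s) over s > r_k.

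**Looks 1 and 2 at p = 0.3.**
- Look 1: P(X ≥ 2 of 3) = 0.189 + 0.027 = 0.216. Continuing: f(0) = 0.343, f(1) = 0.441.
- Look 2: 0.343 × 0.216 + 0.441 × 0.657 = 0.3638. Continuing: f(0) = 0.1176, f(1) = 0.3025.

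**Look 3 at p = 0.3.**
- Six exposed: 0.1176 × P(X ≥ 4 of 6) + 0.3025 × P(X ≥ 3 of 6) = 0.1176 × 0.0705 + 0.3025 × 0.2557 = 0.0856.
- Five exposed: 0.1176 × 0.0308 + 0.3025 × 0.1631 = 0.0530.
- Cumulative by N=12: 0.216 + 0.3638 + 0.0856 = 0.665, against 0.216 + 0.3638 + 0.0530 = 0.633.

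**All four looks.** The last two columns on the right give the chance of suspending at look 3 or 4 once looks 1 and 2 are passed, and the result at a rate of 0.4.

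| Unexposed among patients 7–24 | m_3, m_4 | By N=12, p=0.3 | By N=24, p=0.3 | Given looks 1–2 passed, p=0.3 | By N=24, p=0.4 |
|---|---|---|---|---|---|
| 0 | 6, 12 | 0.665 | 0.842 | 0.624 | 0.974 |
| 2 | 5, 11 | 0.633 | 0.791 | 0.503 | 0.955 |
| 3 | 5, 10 | 0.633 | 0.766 | 0.443 | 0.943 |
| 4 | 5, 9 | 0.633 | 0.740 | 0.382 | 0.929 |

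**Cross-check.** Treating loss as a proportion d of patients at looks 3 and 4 only, so that the DLT probability per accrued patient is 0.3(1 − d), gives 0.842, 0.797 and 0.750 by N=24 for d = 0, 10% and 20%.

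**The same effect as a trigger rate.** Four DLTs in 12 accrued is 33%; with one unexposed it is 4/11 = 36% of those at risk. Six in 24 is 25%; with four unexposed it is 6/20 = 30%.

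**Immature follow-up.** At a look taken on accrual, the newest patient is at least 14 + 42 = 56 days from a complete window under sections 5.1.1 and 5.1.4, or 14 + 28 = 42 days under section 10.4. This adds to the dilution but is not quantified, because it depends on the accrual rate.

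**The case against.** A reader might infer that every look is diluted. The documents do not support that. The looks at 3 and 6 correspond to the 3-to-6-patient safety cohort, for which section 10.4 restricts evaluability to combination recipients, sections 5.1.1, 5.1.4 and 10.4 provide replacement, and section 5.1.1 requires a completed window before Stage 2.

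A reader might also infer that the plan has decided to count unexposed patients. It says no such thing. The Simon paragraph of section 10.5.1 speaks of accruing patients who are evaluable for efficacy, and its total of 24 equals N_4, so the table may have been meant in the same sense. That reading is plausible and would remove the never-exposed patients. However, the Simon paragraph adds the evaluability condition and the DLT legend does not, so two monitors could apply the table differently. Nor would that reading require a completed window.

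Four further points have force:

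- **No documented loss.** The figure of 2 to 4 is an assumption and zero is possible. Sections 5.1.3 and 5.8 tie removal for progression to the period after Day 15, so that rule does not itself remove patients earlier.
- **Little left to suspend at 24.** On the literal reading, enrolment is nearly or fully complete at the last look, although a discussion of amending or closing is still triggered. The look at 12 is the last that protects many later patients, and the loss there is about 3 points.
- **0.3 is the boundary.** At a clearly unacceptable 0.4 the rule still suspends with probability of at least 0.93 in these scenarios.
- **Ongoing review.** Section 10.5.1 also has DLTs monitored every other week, then monthly, then every other month, with a further review at the Stage 1 efficacy analysis. A late DLT can therefore still be counted. This softens the timing point but leaves the denominator undefined.

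**Conclusion.** The point holds for the looks at 12 and 24. As written, their denominator is accrual, while the event being counted requires pembrolizumab exposure, and no DLT-evaluable set or replacement rule applies there.

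The effect is modest. At a rate of 0.3, two to four unexposed patients cost 5 to 10 percentage points of suspension probability by N=24 (0.842 to between 0.791 and 0.740), and one unexposed patient costs about 3 points by N=12. At 0.4 the cost by N=24 is 2 to 5 points. Among trials that pass the first two looks the loss is larger, from 0.624 to between 0.503 and 0.382 at a rate of 0.3.

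These figures rest on an assumed number of losses, full exposure of the first six patients, and the literal reading of accrual. With no loss and complete windows, nothing changes. The rule governs suspension for toxicity, so its denominator should not be left to interpretation.

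**What to change.** First reconcile the DLT window. It is 42 days in sections 5.1.1 and 5.1.4 and 28 days in section 10.4, while the review at the Stage 1 efficacy analysis in section 10.5.1 covers DLTs at any time during therapy. Which applies is for the investigators to settle; evaluability cannot be defined until they have.

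Then, in section 10.5.1, define n_k and N_k at all four looks as patients who have received at least one pembrolizumab dose and have either had a DLT or completed the reconciled window. Take each look when the required number of such patients is reached. Keep the periodic DLT review between looks, so that a safety signal does not wait for the next look. It would also help to state the rule's operating characteristics on this definition: suspension probability 0.501, 0.842 and 0.974 at true rates of 0.2, 0.3 and 0.4.

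The critical values and the efficacy sample size need not change. The cost is the work of reconciling the window, a short amendment to the table legend, and later looks that fall some weeks later in calendar time.
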